#### **Declaration of Interests**

All investigative staff has reported any conflicts of interest to their local IRB as part of the protocol approval process.

#### Access to data

Only authorized personnel, those who have official status as part of the authorized research team, will have access to any records containing identifiable participant data. Study personnel at local sites will only have access to their own site's data, and will be limited by their "user-roles" (i.e. HealthPartners study personnel will only have access to HealthPartners participants, blinded coordinators will not have access to group allocation, or treatment information).

The Clinical Coordinating Center will oversee the intra-study data sharing process.

#### Post-trial care

Participants found to have clinically significant depressive symptoms (PHQ 8 score ≥ 10) at the 18-month visit/interview, will have their PCP and/or cardiologist notified.

#### **Dissemination policy**

Study results will be posted at ClinicalTrials.Gov within one year of study completion. Sites will be encouraged to send each participant a "Thank You" letter upon their completion of study participation. Additionally, it is suggested that, when data is analyzed, a brief lay person summary of the trial results be disseminated through patient communications at each respective site. A Publications and Disseminations Committee will be formed, and this committee will then create a policy/guideline for

authorship and review process of manuscripts and abstracts for publication or conference presentations.

1. SYNOPSIS OF THE STUDY

The goal of this study is to determine the quality-adjusted life year benefits (primary outcome) and health care costs of following the AHA's advisory for depression screening and then referral for further diagnosis and treatment in post-ACS patients, if elevated depressive symptoms are found. To accomplish this aim, we will randomize patients from four different, geographically diverse health systems to three different groups: 1) to the AHA depression screen, notify, and treat if elevated depressive symptoms are found algorithm (Screen, Notify & Treat intervention group) or: 2) to receive no depression screening (No Screen; strong control group) or: 3) to be screened and a primary care provider notified of elevated depressive symptoms (Screen & Notify; minimally enhanced control group). Health-related quality of life, depressive symptoms, and costs will be obtained from all patients, so that the benefits and the costs of these three different depression screening strategies can be compared.

2. STUDY DESIGN AND OBJECTIVES

2.1 Study Design

Investigator initiated, multicenter, 3-group (1:1:1) randomized clinical trial.

2.2 Objectives

The overarching goal of this research is to conduct a state-of-the-art RCT that will rigorously evaluate the benefits and costs of AHA's depression advisory for modern post-ACS patients.

To examine in a randomized controlled trial the benefits and costs of the AHA's advisory for depression screen and treatment of post-ACS patients.

Hypothesis 1: Screen, notify, & treat intervention group will gain significantly more quality-adjusted life years (primary outcome) across 18 months when compared to No Depression screen control group, and also when compared to the Depression screen & notify control group.

Hypothesis 2: Those randomized to AHA's Depression screen & treat intervention group will have a favorable incremental cost-effectiveness ratio when compared to No Depression screen control and also when compared to the Depression screen & notify control group.

3. RANDOMIZATION AND BLINDING

Sequence generation

Participants will be randomly assigned to one of three groups: No Depression Screen, Depression Screen and Notify, or AHA Depression Screen, Notify and Treat. The randomization algorithm will be embedded in the web-based tracking system, using randomly assigned block sizes of 3, 6 and 9.

Concealment Mechanism

Participants will be randomized using the web-based tracking system. "User-roles" are assigned to study personnel, and the randomization tool is only available to unblinded coordinators at each site. Concealment will be ensured as the randomization algorithm will run in the backend, and only the randomization assignment will be visible to the unblinded coordinator after all necessary information about the participant has been entered.

Implementation

All eligible participants who give consent will be randomized by the unblinded coordinator after completion of all baseline assessments. The randomization tool is only available to designated unblinded coordinators (UC) at each site. The UC will enter the required information in the tracking system, after which the participant's group assignment will be immediately available.

If the participant is randomized to the No Depression Screen arm, the UC will inform the participant that no further assessments are required.

If the participant is randomized to the Depression Screen and Notify arm, the UC will administer the PHQ-8. If the PHQ score is ≥ 10, the UC will notify the participant's primary care provider and/or cardiologist either through the tracking system, by email, or mail in accordance with their IRB requirements.

If the participant is randomized to the AHA Depression Screen, Notify, and Treat arm, the UC will administer the PHQ-8. IF the PHQ score is ≥ 10, the UC will inform the patient of the available treatment options. Depending on the participant's choice of treatment, the UC will facilitate the initial contact with the relevant treatment specialist(s), ideally within two weeks of randomization and will work closely with the treatment specialist(s) to monitor the participant's treatment progress. The participant's PCP and/or cardiologist will also be notified of the positive depression screen.

Blinding

The blinded coordinator (BC) will administer all study regular assessments at 6-, 12- and 18-months, and will not be allowed to know the participants' group allocation, and this is ensured by the "user-role" designation in the tracking system. In addition to the UC, and due to the nature of the study treatment, participants, site Pls, and other personnel not designated as BC, cannot be blinded to the group allocation, but are encouraged not to disclose the allocation either at or when assisting the BC in scheduling follow up assessments. After each study visit, the BC will complete a 1-item questionnaire asking if the participant disclosed if they were in treatment. This information will be tracked, however no intervention will occur if the BC becomes unblinded.

4. DEFINITION OF TARGET POPULATION AND STUDY SAMPLES

4.1 Target Population

This study aimed to enroll survivors of acute coronary syndromes without a prior history of depression who had experienced an ACS within the past 2 to 12 months and would be eligible for depression screening.

Detailed eligibility criteria are provided below.

Inclusion Criteria

Criteria	EMR Verification and ICD-9 Codes
English or Spanish*- speaking participants *Spanish-speaking participants eligible at Columbia-site, only	Primary language designation in EMR (if available) Participant attestation

Documented ACS within the past 2-12 months	Evidence of one or more of the following within the past 2-12 months: (1) Diagnosis of acute myocardial infarction (410) during an inpatient hospitalization (2) Diagnosis of unstable angina (411) during an inpatient hospitalization with a history of coronary artery disease (414)
	410.00-410.92 Acute Myocardial Infarction 411.00-411.89 Other acute and sub-acute forms of ischemic heart disease 414.00-414.9 Other forms ischemic heart disease
Over the age of 21 years	DOB
Has access to a phone and/or computer	Participant confirmation of phone number listed in EMR

ICD 9 discharge codes of 410 (acute myocardial infarction) through EMR searches have excellent positive predictive value when clinical data are abstracted and checked by two coders blinded to discharge code. Thus, we will use this discharge code for ACS eligibility. We will furthermore select potential participants with ICD 9 code hospital discharge codes of 411 (unstable angina), who also have established coronary artery disease (ICD 9 code of 414) to ensure that participants meet the definition of an ACS, as described in ACS case definitions by numerous cardiology societies. This approach – having broad eligibility – provides for a high degree of generalizability.

Medical Exclusion Criteria

Terminal illness defined as, but not limited to:		
NYHA class IV, ACC class D CHF requiring inotropes or mechanical assist devices or critical aortic stenosis without plan for correction		
End-stage COPD/emphysema		
Advanced cirrhosis with encephalopathy, varices, severe ascites		
Severe rheumatologic diseases requiring frequent hospitalizations, and multiple cytotoxic		
agents and/or disease modifying drugs		
Metastatic pancreatic, esophageal, colorectal or stomach cancer		
Metastatic sarcoma, ovarian, melanoma or renal cell cancer		
Metastatic breast cancer with multiple recurrences despite treatment		
Advanced CNS malignancies		
Recurrent hematologic malignancies with multiple recurrences despite treatment		
Persistent AIDS, untreated or treated		
Currently pregnant		

Participant Reported Screening Exclusions

Potential participants will complete a brief screening questionnaire to confirm that they have none of the above conditions, that they speak English and that they are interested in being enrolled in the study

4.2 Intent-to-Treat Sample

Analyses will be conducted on an intent-to-treat sample. No analyses will be conducted on a per-protocol or safety analysis sample.

4.3. Safety Analysis Sample

Safety analyses will be conducted using the same sample as the primary efficacy sample, and an intent-to-treat analysis plan will be used.

5. DESIGN CONSIDERATION

5.1 Primary Statistical Hypothesis

Those randomized to AHA's Depression Screen, Notify & Treat intervention group will gain significantly more quality-adjusted life years across 18 months when compared to No Depression Screen control group, and also when compared to the Depression Screen & Notify control group.

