#### Sample Size

For the primary outcome in Aim 1, we will be making two primary comparisons: Difference in QALYs comparing AHA's Screen, Notify & Treat group vs. Screen & Notify and then separately to No Screen group. For choosing a sample size, we assumed a standard deviation for QALYs in the conservative control group (e.g., no depression screen) of 0.17. Additionally, based on a prior study of management of depression for patients with cancer, we assumed a net improvement in QALYs of 0.155 over 18 months of follow-up for individuals receiving the AHA's screen & treat intervention would be reasonable to expect. We assumed a 0.055 gain in QALYs for all participants not receiving treatment (i.e., those in the No Screen group, the Screen & Notify group and those without depression in the AHA's Screen, Notify & Treat group). An important consideration for this trial is that only 20% of patients randomized to the AHA's Screen, Notify & Treat group will meet criteria for depression and thus will receive the treatment part of intervention. Therefore, assuming an improvement in QALYs of 0.21 (0.055 background improvement + net improvement of 0.155) over the 18-month follow-up period for the 20% of participants with diagnosed depression and a 0.055 improvement in QALYs for the 80% of participants in this randomization group without depression, an overall gain in QALYs of 0.086 over the 18-month follow-up period can be anticipated in

\*\* For blinded coordinator only

\*Only completed if necessary

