this randomization group (0.21 \* 0.2 + 0.055 \*0.8 = 0.086). Thus, we anticipate a relative difference in QALYs of 0.031 (0.086 change in the AHA's screen & treat group minus 0.055 in the no screen group). We will have 80% statistical power to detect this difference of 0.031 with a sample size of n=475 participants in each group. We chose to determine sample size based on a pairwise comparison at 80% power in the two-step procedure, as a conservative approach relative to powering based on the F-test (See Statistical Analysis section, below, for further details). Specifically, under the scenario where one group has higher QALY than the other two by an effect size 0.18, the F-test will yield 84% power. Adding in 5% loss to follow-up, we selected an overall sample size of n=500 in each randomization group for an overall sample size of n=1500. Power analyses are typically based on the primary clinical outcome. We selected the QALY as our primary outcome and did not have specific economic hypotheses that required statistically tests. Therefore, we chose to follow this tradition, and do not present power calculations for our incremental cost-effectiveness ratios.

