5.4 Sample Size Determination

The sample size of the trial was determined based on an assumed standard deviation for QALYs of 0.17.5 Additionally, based on a general health-related quality of life outcome in a prior study of management of depression for patients with cancer, we assumed a net improvement in QALYs of 0.155 over 18 months of follow-up for depressed individuals who receive depression treatment in the Screen, Notify and Treat group.6 We assumed a 0.055 gain in QALYs for all patients not directly linked to depression treatment (i.e., those in the No Screen group, the Screen & Notify group and those without elevated depressive symptoms in the Screen, Notify, and Treat group). An important consideration for this trial is that only 20% of patients randomized to the Screen. Notify and Treat group were expected to meet criteria for elevated depressive symptoms and thus, to receive depression treatment. Therefore, assuming an increase in QALYs of 0.21 (0.055 background improvement + net improvement of 0.155) over the 18-month follow-up period for the 20% of patients diagnosed and treated for depression in the Screen, Notify, and Treat group and a 0.055 improvement in QALYs for the 80% of patients in this randomization group without depression, an overall gain in QALYs of 0.086 over the 18 month follow-up period was anticipated in this randomization group (0.21 * 0.2 + 0.055 * 0.8 = 0.086). Thus, we anticipated a difference in QALYs of 0.031 (0.086 change in the Screen. Notify, and Treat group minus 0.055 in the No Screen group or Screen and Notify Group), leading to an expected effect size of 0.18 (= 0.031/0.17). With this effect size, we determined the sample size per group to be 475, which would yield 80% power for a two-sided t-test at 5% level. We chose to determine sample size based on a pairwise comparison at 80% power in the two-step procedure (described above), as a conservative approach relative to powering based on the F-test. Specifically, under the scenario where one group has higher QALY than the other two by an effect size 0.18, the F-test will yield 84% power. Adding in 5% loss to follow-up, we selected an overall sample size of n=500 in each randomization group for an overall sample size of n=1500.

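### The stated 80% is the power of one t-test alone; in the planned two-step procedure a named comparison has about 76%, and Hypothesis 1 as worded (superiority over both controls) about 68%

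*SAP*

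**What the plan says.** **The hypothesis.** SAP 5.1 states one primary hypothesis: the intervention gains significantly more QALYs "when compared to No Depression Screen control group, and also when compared to the Depression Screen & Notify control group". SAP 2.2 and the protocol (Objectives/Hypothesis; Statistical Methods, Hypothesis 1) carry the same two-part claim.

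**The comparisons.** The protocol's Sample Size section reads "For the primary outcome in Aim 1, we will be making two primary comparisons" and lists them as "Screen, Notify & Treat group vs. Screen & Notify and then separately to No Screen group".

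**The test.** SAP 5.3 and the protocol's Statistical Methods prescribe a one-way ANOVA F-test at 5%. All three pairwise two-sided t-tests at 5% follow only if the F-test is significant. Both places give the aim of the primary analysis as finding whether the three groups differ.

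**The power.** In SAP 5.4, "we anticipated a difference in QALYs of 0.031" is the assumed effect, with SD 0.17 and 475 per arm, "which would yield 80% power for a two-sided t-test at 5% level". The basis is given as "We chose to determine sample size based on a pairwise comparison at 80% power in the two-step procedure", described as conservative relative to the F-test, for which 84% is quoted. The comparator gain is "0.055 in the No Screen group or Screen and Notify Group", so the two controls are assumed identical.

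**The concern.** Three things do not line up.

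- **Hypothesis and power.** The hypothesis joins two superiority claims, but power is given for one.
- **Procedure and power.** The 80% is described as belonging to a pairwise comparison in the two-step procedure. It is actually the power of the t-test alone. A comparison that must also wait for a significant F-test has less.
- **Control arms.** The same 0.031 is used against Screen & Notify. That arm differs from No Screen in that patients are screened and the doctor is told of a positive result. The calculation gives this no benefit at all.

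At stake is how a split result would be read. If the intervention beats one control and not the other, the plan does not say whether Hypothesis 1 has been met, and either answer could be argued once the data are known. A reader who takes 80% as the chance of confirming the hypothesis as worded would also be misled.

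**Working it through.** **Inputs (SAP 5.4; allocation from SAP 2.1).** Difference 0.031 (0.086 − 0.055), SD 0.17, two-sided 5%, 1:1:1 allocation, 475 evaluable per arm, 500 randomized per arm, same 0.055 gain in both controls.

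**Step 1: the plan's own figures.**
- n per arm = 2 × (1.960 + 0.842)² × (0.17/0.031)² ≈ 473, against 475 stated.
- Effect size = 0.031/0.17 = 0.1824. Noncentrality at 475 = 0.1824 × √(475/2) = 2.810. Power = Φ(2.810 − 1.960) = 80.2%.
- 475/0.95 = 500.
- F-test: λ = 475 × 0.1824² × 2/3 ≈ 10.53 on 2 and 1422 df, giving 83.5% (82.5% with the rounded 0.18), against 84% stated.

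The stated figures reproduce.

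**Step 2: both comparisons, t-tests alone.** The two statistics share the intervention arm, so with equal arms their correlation is 0.5. Power for both = Φ₂(0.850, 0.850; ρ = 0.5) = 69.0%. At 500 per arm it is 71.8%.

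**Step 3: the full two-step procedure.** Simulated with 2 million replicates (F-test at 5%, then two-sided t-tests at 5%, counting results in favour of the intervention):

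| Criterion | 475, t-test alone | 475, two-step | 500, two-step |
|---|---|---|---|
| One named comparison | 80.2% | 76.0% | 78% |
| Both comparisons | 69.0% | 68.4% | 71.1% |
| At least one | – | 83.5% | 85.4% |

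Requiring the F-test costs a named comparison 80.2 − 76.0 = 4.2 points: trials in which that t-test is significant but the F-test is not. It costs the both-significant criterion only 0.6 point. Using the pooled three-arm variance in the t-tests leaves the 68.4% unchanged.

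Under the plan's assumptions, exactly one of the two comparisons is significant in 83.5 − 68.4 ≈ 15% of trials.

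**Step 4: if notification helps.** The documents give no figure for this, so the shares below are an assumption. Two-step power at 475 per arm (1 million replicates each):

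| Share of the 0.031 achieved by Screen & Notify | vs Screen & Notify | vs No Screen | Both | At least one |
|---|---|---|---|---|
| 0% (plan) | 76% | 76% | 68% | 83.5% |
| 10% | 67% | 74% | 62% | 80% |
| 25% | 53% | 72% | 50% | 75% |
| 50% | 28% | 70% | 27% | 70% |

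Power against No Screen falls too, although that difference stays at 0.031, because the F-test loses power when the middle arm moves up.

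**The case against.** The strongest reply is that no section adopts a both-must-win rule. The protocol speaks of two comparisons made separately. SAP 5.3 and 5.5 rely on strong familywise error control, which is what one needs to claim comparisons one at a time; if both had to succeed, each could be tested at 5% with no adjustment. The stated aim of the primary analysis is a difference among three groups, which is the F-test, and that has about 84%. The joining words in the hypothesis could simply list two predictions.

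This stands in large part. A reader might infer that both comparisons must be significant and that the trial is therefore underpowered against its own target. The documents do not support that: the wording allows the reading, but other sections point elsewhere. A reader might also infer that the 80% is a mistake. It is not: sizing on one comparison is disclosed ("We chose to determine sample size based on a pairwise comparison at 80% power"), and the figure is right for the t-test it names. The equal gain in the two controls is also stated openly, and the 10%, 25% and 50% shares have no source in the documents.

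What the reply leaves unanswered is narrower. A significant F-test alone does not show that the intervention beats either control, which is what Hypothesis 1 claims. Under the separate-claims reading, each claim still has to pass the F-test first, so its power is about 76%. Calling the pairwise basis conservative is true only relative to the F-test. It is true that all three pairwise results will be produced whatever the label, so a split result would be visible; what is missing is the rule for interpreting it.

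**Conclusion.** The point holds in limited form. The 80% is delivered neither for the hypothesis as worded (about 68%, two-step) nor for a named comparison in the planned procedure (about 76%). Only the F-test or an at-least-one rule reaches 80% (both about 83.5%).

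These figures rest on the plan's difference of 0.031, SD of 0.17, 475 evaluable per arm and zero effect of notification. A reader might take 69% as a ceiling for winning both. It is not: if all 500 per arm contributed full information, the figure would be 71% two-step or 72% without the F-test. The Screen & Notify figure is an upper bound at those inputs in the sense that any benefit of notification lowers it. How far it falls depends on an assumption that the documents do not inform, so Step 4 shows sensitivity and is not a forecast.

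No estimate, error rate or sample size is wrong. This is a correction to the power statement plus a missing success rule.

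**What to change.** 1. **SAP 5.1 and protocol Hypothesis 1:** add one sentence giving the success rule. For example: Treat vs No Screen and Treat vs Screen & Notify are two separately claimable comparisons, each established if the F-test and its own two-sided t-test are significant at 5% in favour of the intervention. If both are required instead, say so. The rule should be dated and settled without sight of results by arm.
2. **SAP 5.4 and protocol Sample Size:** keep 475 and 500 per arm. Replace the 80% attributed to the two-step procedure with about 76% per named comparison, and about 68% if both are required. The 80% may stay if labelled as the power of the t-test alone.
3. **Same sections:** state that the Screen & Notify figure assumes no benefit from notification and is an upper bound. Add the short table from Step 4 with its shares labelled as assumptions.

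The cost is wording and one small table. The downside is a less favourable power statement. No new data, analyses or patients are needed.

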5.2 Interim and Final Primary Analysis

Given the nature of a screening trial, no *a priori* stopping rules were planned. Interim analyses were planned for purposes of monitoring the study for safety concerns, only.

